Planned number of study subjects	
At Stage 1, 53 volunteers are planned to be screened (taking into consideration supposed withdrawal of 18 subjects - 50% of planned number of subjects included at screening stage) which will result in inclusion of totally 35 healthy volunteers complying with inclusion criteria: 6 male volunteers of the main group into each of 5 cohorts of single dosing and one back-up in each cohort at the first stage.
 
At Stage 2, 30 volunteers are planned to be screened (taking into consideration supposed withdrawal of 15 subjects - 50% of planned maximum number of subjects included at screening stage) which will result in inclusion of totally up to 20 healthy volunteers complying with inclusion criteria: 6 male volunteers of the main group into each of 2 cohorts of multiple dosing (C6 and C7) with possible additional inclusion of 4 volunteers into each cohort in case of withdrawal at the second stage.

	
Total number of screened volunteers during the both study stages will be up to 83 subjects.
 
Total number of volunteers included at the both study stages will be up to 55 subjects.
 
As the main tasks of this study are safety and tolerance evaluation and the study is not comparative in design, acceptable from this point of view sample size for such clinical studies has been chosen which allows, first of all, to study safety and tolerance profile of the test drug.

Selection criteria	
At each of two stages, healthy male volunteers aged 18 to 45 years old are planned to be included into the study according to inclusion criteria with no non-inclusion criteria. Similar selection criteria are used for all cohorts.

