Inclusion criteria	
Volunteers complying with each of the following criteria will be included into the clinical study:
 
1. Written informed consent received from a volunteer.2. Men aged 18 to 45 years old, inclusive.3. Body mass index of 18.5–25 kg/m².4. Verified diagnosis: "healthy" according to data of standard clinical, laboratory and instrumental examination methods performed at screening:
• Absence of deviations of physical examination parameters and vital signs (systolic blood pressure - 100–129 mm Hg, inclusive; diastolic blood pressure - 70–89 mm Hg, inclusive; heart rate - 60–80 bpm, inclusive);• Absence of deviations of laboratory parameters (complete blood count, blood biochemistry, HIV, HBV, HCV, syphilis and urinalysis);• Normal parameters of 12-lead ECG;• Normal results of photofluorographic or X-ray examination (the results received maximum 6 months before screening can be used);• Normal blood glucose levels during the oral glucose tolerance test (less than 5.6 mmol/l at fasting state and less than 7.8 mmol/l 2 hours after glucose charge). This test is only used for volunteer inclusion screening in cohorts with multiple dosing.5. Ability, according to investigator, to comply with all requirements of the protocol.6. Agreement to use double contraception method during the study participation and for 3 months after the test drug administration - combination of male condom with not less than one of the following methods:
• female partner using hormonal contraception;• using aerosols, creams, suppositories and other agents containing spermicides;• female partner using intrauterine device.
Non-inclusion criteria	
Volunteers who will comply with at least one of the following criteria will not be included in the clinical study:

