	
 1. Aggravated allergic history, including presence of at least one episode of drug allergy. 2. Chronic diseases of cardiovascular, bronchopulmonary, neuroendocrine systems, ENT and gastrointestinal, hepatic, renal, blood and cutaneous diseases. 3. Chronic diseases of eyes except for myopia, hypermetropia and mild to moderate astigmatism. 4. Gastrointestinal surgeries (except for appendectomy performed not more than 1 year before screening). 5. Acute infections within less than 4 weeks before screening. 6. Regular drug administration within less than 4 weeks before screening. 7. Regular administration or application (including topical) of hormonal drugs for more than 1 week within less than 45 days before the screening. 8. Administration of drugs exerting evident effects on hemodynamics, hepatic function, etc. (barbiturates, omeprazole, cimetidine, etc.) within less than 45 days before the screening. 9. Positive test for narcotic and psychotropic agents. 10. Donation (450 mL of blood or plasma) within less than 3 months before the screening. 11. Intake of more than 10 U of alcohol per week (1 unit of alcohol is equivalent to 500 mL of beer, 200 mL of vine or 50 mL of strong alcoholic drink) or historical data on alcoholism, narcomania, drug abuse. 12. Mental illnesses. 13. Smoking within half a year before the screening. 14. Previous participation in this clinical study and withdrawal from it due to any reason. 15. Participation in other clinical studies of drugs within less than 6 months before the screening. 16. Planned conception or sperm donation during the study after the test drug administration or during 3 months after the date of the last drug administration.
Withdrawal criteria	
Withdrawal criteria should be considered as follows:
 
 1. Volunteer's refusal to participate in the study at any stage of its performance. 2. Occurrence of adverse event, including serious adverse event: individual intolerance of the test drug, hypersensitivity to the drug ingredients found directly in the drugs administration due to which further participation in the study is not possible. 3. Intolerance of the study procedures by a volunteer. 4. Any event or volunteer's condition which, according to investigator, makes further participation of the volunteer in

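### Non-inclusion item 4 exempts only a recent appendectomy: it is apparently reversed relative to every other look-back limit in the list, and no reason is given

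*Combined protocol and SAP*

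**What the plan says.** All of this stands in section 1, Study summary.

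- **Effect of a non-inclusion criterion.** One is enough to keep a volunteer out: "Volunteers who will comply with at least one of the following criteria will not be included in the clinical study".
- **Item 4.** Gastrointestinal surgery is such a criterion, with no look-back limit of its own. The single carve-out reads "except for appendectomy performed not more than 1 year before screening".
- **Other time-limited items.** Examples are item 5, "Acute infections within less than 4 weeks before screening", item 10, "Donation (450 mL of blood or plasma) within less than 3 months before the screening", item 13, "Smoking within half a year before the screening", and item 15, "Participation in other clinical studies of drugs within less than 6 months before the screening".
- **Scope.** The Selection criteria row says "Similar selection criteria are used for all cohorts", so item 4 applies in both stages. Three centers are planned.
- **Consequence of a breach.** Under Withdrawal criteria, item 8 makes enrolment against the inclusion or non-inclusion criteria a ground for withdrawal. The same section lists it among the reasons that allow substitution. One volunteer may be substituted in each of C1-C5. In C6-C7 substitution needs at least two withdrawals.

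**The concern.** An exception to a surgical exclusion normally marks the cases that the plan regards as harmless. Here the exempt case is the recent operation and the barred case is the old one, the opposite of how the rest of the list treats time. The rule gives a yes or no answer for each volunteer with this history, so its direction decides who enters.

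Two things are at stake. First, the study gives oral capsules to humans for the first time, and its variables include Cmax, Tmax and an absorption-rate ratio, so a criterion on gastrointestinal surgery bears on what is measured. Second, a center that follows the words and a center that follows what it takes to be the intention would reach opposite decisions on the same man. The second center would be recording a breach of a written criterion.

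**Working it through.** No sample size, power or event count is involved, and the plan gives no figure to reproduce. The check is a reading of the rule.

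**Step 1: item 4 taken literally.** Let t be the time from appendectomy to screening. Item 4 excludes gastrointestinal surgery unless it is an appendectomy with t ≤ 1 year.

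- t = 6 months: inside the exception, not excluded by item 4.
- t = 10 years: outside the exception, excluded by item 4.

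**Step 2: comparison with every other look-back item in the list.**

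| Item | Subject | Window before screening | Recent event | Older event |
|---|---|---|---|---|
| 4 | Appendectomy | 1 year | accepted | excluded |
| 5 | Acute infection | 4 weeks | excluded | accepted |
| 6 | Regular drug use | 4 weeks | excluded | accepted |
| 7 | Hormonal drugs for over 1 week | 45 days | excluded | accepted |
| 8 | Drugs with marked hemodynamic or hepatic effects | 45 days | excluded | accepted |
| 10 | Blood or plasma donation | 3 months | excluded | accepted |
| 13 | Smoking | half a year | excluded | accepted |
| 15 | Other drug trials | 6 months | excluded | accepted |

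Seven of seven comparators run one way; item 4 runs the other.

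**Step 3: do other criteria undo the effect?**

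- *First weeks after surgery.* Inclusion item 4 requires a verified healthy status, with no deviations on examination, vital signs or laboratory tests. Non-inclusion items 5 and 6 exclude acute infection and regular drug use within 4 weeks. Together these would stop many such men. Item 8 could reach back to 45 days if drugs given around the operation fall within its class, which the plan does not address.
- *From about 4 weeks to 12 months.* No other criterion is aimed at recent surgery. A man who has recovered and tests normal can pass.
- *More than 12 months.* No provision readmits a healthy man with an old appendectomy. Item 4 alone excludes him.

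**Step 4: what follows if a center applies the presumed intention.** Suppose it enrols a man with an older appendectomy. He meets a written non-inclusion criterion, so withdrawal item 8 applies. In C1-C5 the cohort's one back-up can replace him, within the window the plan sets. In C6-C7 a lone withdrawal is not replaced, so the cohort would continue with 6 − 1 = 5 volunteers.

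**The case against.** The best counter-argument is that the intent is being guessed. Items 5, 6, 7, 8, 10, 13 and 15 are exclusions with a look-back window. Item 4 is an unlimited exclusion with a time-limited exception, the only one of that form in the list, so the parallel is imperfect. This stands: the comparison makes a slip plausible and does not prove one. A reader might infer that the criterion is a demonstrated error; the documents support only that it is apparently reversed and unexplained.

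It can also be said that this is a language slip which sites will read sensibly. The text has others, such as a human equivalent dose given in mg/h where the calculation is in mg/kg. Sites may also work from another language version, though the documents do not say so. If it is a slip, that is a reason to correct it. Leaving each center to guess is what produces inconsistent decisions.

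A reader might further infer that men only weeks out of surgery can walk into the study. Item 4 taken alone would allow that, but the healthy-status requirement and items 5 and 6 block much of it. The open interval is the later one shown in step 3.

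Finally, one volunteer is 1/6 = 16.7% of a cohort, and it is tempting to quote that as the size of the problem. It should not be used so. The ratio holds for any volunteer lost for any reason, says nothing about how often this criterion applies, and ignores the back-up in each of C1-C5.

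**Conclusion.** The point holds as a wording defect in an operative eligibility rule. As written, item 4 accepts the recent appendectomy and excludes the older one, against the direction of all seven other look-back limits, and no reason is offered. Other criteria cover part of the recent side and none of the older side.

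The weight is minor. The documents do not say how many volunteers would have this history; among up to 55 included it is probably few. That is a judgement, not a calculation. The planned sample size and the analysis are unaffected, and no bias in the safety or pharmacokinetic results is shown. The practical exposure is inconsistent screening across three centers and, in C6-C7, an eligibility withdrawal that the replacement rule does not make good.

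The conclusion assumes that centers screen from this wording, as it stands in section 1.

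**What to change.** The sponsor should confirm which direction the 1-year limit is meant to run. Then either reword item 4 so that it is reconciled with the other recency limits in the list, or keep it and add a sentence saying why a recent appendectomy is acceptable and an older one is not. This review does not say which limit is right. The same wording should be used wherever the criterion is repeated and in any other language version in use.

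The cost is one phrase or one sentence in the protocol. No sample size, schedule or analysis text changes.

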According to the results of the analysis of all the data obtained after the completion of the study by all volunteers from cohorts 1 to 5, a clinical study report will be prepared.

Stage 2 (multiple dosing with dose escalation)

Up to 3 cohorts are planned to be enrolled during the second stage of the study with 6 subjects in each to investigate the drug after multiple administration.

Volunteers complying with the study inclusion criteria will be included successively into the following cohorts for multiple drug administration:

- Cohort 6 (C6) includes 6 healthy volunteers each of whom will receive X* mg of PBTZ169 daily under fasting conditions once a day in the morning at the same time ±15 min for 14 days.
- Cohort 7 (C7) includes 6 healthy volunteers each of whom will receive Y* mg of PBTZ169 daily under fasting conditions once a day in the morning at the same time ±15 min for 14 days.

*The dose of PBTZ-169 will be defined taking into account the results of the data analysis and the conclusions of the independent Committee for data evaluation and study subjects' safety.

The same inclusion criteria will be used to select volunteers into cohorts C6-C7 as those used to select volunteers into Cohorts 1-5.

If two or more volunteers drop out from multiple administration cohorts before the study Day 7 inclusive due to different reasons, except for AE/SAE, according to Sponsor's decision, volunteers can be additionally enrolled by the number of drop outs for whom an additional screening will be performed. Up to 4 back up volunteers are supposed to be additionally required for each of multiple dosing cohorts. If back-up is necessary in multiple dosing cohort, the period of hospitalization and all the study procedures for a back up will be equivalent to those for substituted volunteer.

Screening procedures to include volunteers into each cohort will be performed within 10 days before the drug prescription.

Screening of volunteers into Cohort 7 can be started not earlier than 24 h after all the volunteers from the previous cohort have received the last dose of the drug.

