	
the study impossible.
 
5. Misbehavior of a volunteer (including if the volunteer was admitted to hospital later than appointed), loss of contact with a volunteer (including due to change of residence).6. Intake of alcohol or products containing grapefruit, pomelo, cranberry and their juices is prohibited 72 h before the drug administration and further till the end of participation in the study.7. Vomiting during the first 4 hours after the drug administration.8. Inclusion of volunteer into the study in case of incompliance with the inclusion/non-inclusion criteria.9. Study termination by the Sponsor.10. Study termination by the Investigator.11. Study termination by the Regulatory Authorities. 
If patient is withdrawn from the study due to any reason, all biosamples collected will be analyzed and investigators will make attempts to obtain maximum complete information on volunteer (including collection of biosamples and clinical information unless informed consent is withdrawn) to assure his safety.
 
If a volunteer is withdrawn from the study cohorts C1-C7 before dosing and during 4 months since dosing (for volunteers of C1-C5) or before the end of visit on the drug administration day 7 (for volunteers of C6-C7) due to the following reasons, a withdrawn patient can be substituted with a back-up according to the Investigator:
 
1. Refusal of a volunteer to participate in the study.2. Intolerance of study procedures by a volunteer.3. Any event or volunteer's condition which, according to investigator, makes further participation of the volunteer in the study impossible.4. Misbehavior of a volunteer (including if the volunteer was admitted to hospital later than appointed), loss of contact with a volunteer (including due to change of residence).5. Intake of alcohol or products containing grapefruit, pomelo, cranberry and their juices is prohibited 72 h before the drug administration and further till the end of participation in the study.6. Inclusion of volunteer into the study in case of incompliance with the inclusion/non-inclusion criteria. 
Substitution of 1 volunteer is possible in each of cohorts C1-C5. In each of cohorts C6-C7, a volunteer can be substituted only if two or more volunteers are withdrawn while the substitution will not be performed if 1 volunteer is withdrawn.

--	---

Test drug	PBTZ169 capsules for oral administration, 40 mg

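### In Cohorts 6 and 7 a single volunteer lost before the first dose cannot be replaced, so a cohort planned at 6 is dosed with 5, although two to four such losses may be made good

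*Combined protocol and SAP*

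**What the plan says.** All references are to Section 1, Study Summary, of the combined protocol and SAP.

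- **Planned size.** Design and methodology, Stage 2: "Cohort 6 (C6) includes 6 healthy volunteers each of whom will receive X* mg of PBTZ169 daily", and "Cohort 7 (C7) includes 6 healthy volunteers each of whom will receive Y* mg of PBTZ169 daily". Planned number of study subjects repeats 6 per cohort, with up to 4 additional volunteers in each if there are withdrawals.
- **Substitution window.** Withdrawal criteria: the sentence opens "If a volunteer is withdrawn from the study cohorts C1-C7 before dosing" and, for the multiple-dose cohorts, runs to "before the end of visit on the drug administration day 7 (for volunteers of C6-C7". The listed reasons include refusal, late arrival at hospital, use of alcohol or certain fruit products from 72 h before dosing, and inclusion in breach of the criteria.
- **Threshold.** The same row then limits this for C6-C7: anyone lost "can be substituted only if two or more volunteers are withdrawn while the substitution will not be performed if 1 volunteer is withdrawn". Design and methodology agrees: "If two or more volunteers drop out from multiple administration cohorts before the study Day 7 inclusive due to different reasons, except for AE/SAE", then, if the Sponsor so decides, "volunteers can be additionally enrolled by the number of drop outs".
- **Stage 1, for contrast.** Each of C1-C5 may replace one volunteer, and one back-up is admitted with the cohort.

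**The concern.** A tolerance of one drop-out is understandable once a volunteer has been dosed, because he has already contributed some data. The rule, however, runs from before the first dose to Day 7 and treats an undosed volunteer in the same way. Under Statistical methods, someone who never takes the drug is in neither the safety population nor the multiple-dose PK population, so his place yields nothing.

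The situation can plausibly arise. Stage 2 screening may take place up to 10 days before dosing, admission is on the evening of Day 0, and the first dose follows on Day 1. Several of the listed withdrawal reasons can occur in that interval.

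At stake is one of six exposed volunteers in cohorts that are the trial's only source of repeated-dose data. The C6 result also decides whether C7 may start.

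**Working it through.** **1. The plan's own totals.** Stage 2 maximum: 2 × (6 + 4) = 20. Overall maximum: 5 × 7 + 20 = 55. Both match Planned number of study subjects. The plan gives no power or precision calculation to reproduce.

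**2. The rule applied to losses before the first dose.** Let L be the number lost out of 6. If L is 0 or 1, the cohort starts with 6 − L. If L is 2 or more, it can start with up to 6 − L + min(L, 4), where 4 is the number of extra places per cohort.

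| Lost before dose 1 | Dosed (maximum allowed) |
|---|---|
| 0 | 6 |
| 1 | 5 |
| 2, 3 or 4 | 6 |
| 5 | 5 |
| 6 | 4 |

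One loss gives a smaller cohort than two, three or four losses if the permitted replacements are made.

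**3. Does the window include the pre-dose period?** The before-dosing phrase could be attached only to the C1-C5 part of an awkward sentence. Even then, the C6-C7 limit is the end of the Day 7 visit, with no starting point, and the Design and methodology wording also sets only an end point. Both cover the time before dose 1, and late hospital admission is itself a listed reason.

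**4. What 5 instead of 6 does.**

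- Chance of seeing no case of an event with 20% risk: 0.8^6 = 0.262 with 6, and 0.8^5 = 0.328 with 5.
- Starting C7 requires DLT in less than 50% of C6. With 6, 2/6 = 33% passes and 3/6 = 50% does not. With 5, 2/5 = 40% passes and 3/5 = 60% does not. Three volunteers are needed to stop at either size.
- Chance of 3 or more DLTs at an assumed true rate of 30%:
  - n = 6: 1 − (0.7^6 + 6 × 0.3 × 0.7^5 + 15 × 0.3^2 × 0.7^4) = 1 − 0.744 = 0.256.
  - n = 5: 1 − (0.7^5 + 5 × 0.3 × 0.7^4 + 10 × 0.3^2 × 0.7^3) = 1 − 0.837 = 0.163.

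**5. How often.** The documents give no pre-dose loss rate. If each volunteer independently has probability p of being lost before dosing, the chance of exactly one loss in six is 6p(1 − p)^5.

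| Assumed p | Exactly one lost, per cohort | In at least one of the two cohorts |
|---|---|---|
| 2% | 10.8% | 20.5% |
| 5% | 23.2% | 41.0% |
| 10% | 35.4% | 58.3% |

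The last column is 1 − (1 − P)^2, where P is the per-cohort chance before rounding.

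**6. Room for a substitute.** One replacement per cohort means 12 + 2 = 14 volunteers, within the maximum of 20. The screening figures do not reconcile (30 screened less 15 lost is 15, not 20), but 14 fits under either number.

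**The case against.** The threshold is stated twice and consistently, and the bar on replacing one volunteer is explicit. The sponsor may knowingly accept 5. Six is a planned number chosen pragmatically, with no precision target. This stands: the point concerns a design choice that could be better, and the rule breaks no guarantee.

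The rule also has a purpose, so the inference that it saves nothing is unsupported. Replacement requires additional screening and a 16-day hospital stay. C7 cannot be dosed until 7 days after every C6 volunteer has taken the last dose, so a late C6 substitute can hold up C7. This stands as a cost, although the plan already accepts it when two or more are replaced.

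A single loss after dosing but before dose 7 also leaves 5 in the multiple-dose PK population, and limiting the rule to post-dose withdrawals does not change that. This stands too. The case for treating the undosed volunteer differently rests on safety exposure and the planned number dosed; PK alone would not make it.

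Other stronger readings also fail:

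- A reader might infer that the DLT criterion is loosened from 33% to 40%. The count needed to stop is 3 at both sizes; only the chance of reaching it changes.
- A reader might cite a wider confidence interval. Statistical methods plans descriptive statistics only.
- A reader might take two losses as always restored to 6. Replacement is permitted, not required: one section leaves it to the Sponsor, the other to the Investigator.

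**Conclusion.** The concern holds, with a modest consequence. Both sections apply the two-or-more threshold to pre-dose losses, and nothing exempts an undosed volunteer. One such loss leaves 5 dosed, while two to four may be restored to 6.

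The price is one fewer exposed volunteer in a descriptive cohort: a 33% rather than 26% chance of missing an event with 20% risk, and a 16.3% rather than 25.6% chance of reaching 3 DLTs if the true rate is 30%. The event risk and DLT rate are illustrative. The frequency of 11% to 35% of cohorts depends entirely on assumed independent loss rates of 2% to 10%. No power calculation is affected, and the documents do not support a claim that the trial's conclusions are compromised. It is worth correcting because the correction is cheap.

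**What to change.** In both the Withdrawal criteria and the Stage 2 part of Design and methodology, limit the two-or-more condition to withdrawals after the first dose. Add that any C6-C7 volunteer withdrawn before the first dose may be replaced by an already screened, eligible volunteer, whatever the number lost, within the 4 extra places per cohort. The same edit should settle whether the Sponsor or the Investigator decides, and square the use of an already screened volunteer with the present provision for additional screening.

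The cost is a sentence in each of two places. The planned 6 dosed per cohort and the Stage 2 maximum of 20 do not change. In practice it needs either one eligible stand-by per cohort or a substitute who starts later, who may need additional screening and may delay C7.

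If the sponsor prefers to keep the rule, state in Design and methodology and in Planned number of study subjects that a Stage 2 cohort may be dosed with fewer than 6.

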Before and after the administration of the first, 7th and last (14th) dose of the test drug, venous blood will be taken from the volunteers to determine PBTZ169 concentration at the following time points: before the first drug dose administration: 0 min (before the drug administration) and for 24 h after the administration of the first, 7th and last (14th) dose of the test drug in: 0:15, 0:30, 0:45, 1:00, 1:30, 2:00, 3:00, 4:00, 6:00, 8:00, 10:00, 12:00, 24:00 (h:min after the drug dosing). 24 h point after the administration of 1 and 7 drug doses should be taken before the successive doses. During drug administration days 3-6 and 9-13, venous blood will be daily taken at 0 min time point (before the drug administration) to determine PBTZ169 concentration. Blood will be sampled at 48 h and 72 h time points after the administration of the last (14) drug dose.

The deviations from the specified time by 10 min to one or another side (\pm 10 min) are acceptable for the following time points: 24 hours for administration of the first, 7th and last (14th) doses of the test drug. For 48 h and 72 h time points after the last (14th) dose administration, deviation from the specified time by 20 min to one or another side (\pm 20 min) is acceptable. For the rest time points, blood sampling after the test drug administration can deviate by not more than 2 min to one or another side (\pm 20 min).

In case of preterm withdrawal from the study, if there is no risk for a volunteers, attempts to sample their blood according to schedule for the last (14) dose will be taken.

At every time point of blood sampling for PBTZ169

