	
Pharmacokinetic parameters evaluated (multiple dosing)
 
 • Maximum concentration (C_{max}) • Maximum steady-state concentration ($C_{max,ss}$) • Trough concentration after multiple administration (C_{trough}) • Time to maximum concentration (T_{max}) • Time to maximum steady-state concentration ($T_{max,ss}$) • Area under the concentration-time curve from 0 to last blood sampling (t) (AUC_{0-t}) • Area under the concentration-time curve from zero to infinity ($AUC_{0-\infty}$) • Steady-state area under the concentration-time curve (AUC_{ss}) • Total clearance (Cl_t) • Renal clearance (Cl_{ren}) • Apparent distribution volume (V_d) • Steady-state distribution volume (V_{ss}) • Half-life ($T_{1/2}$) • Mean retention time (MRT) • Elimination constant k_{el}
Statistical methods	
The study results will be statistically analyzed in the following populations:
 
 • Intent-to-treat population - comprises of all the participants who underwent screening and comply with all the selection criteria. The population will be used for listings and presentation of data by participants' disposition. • Safety population - consists of participants who administered the test drug (for Cohorts C6-C7 - at least once). It will be used for analysis and evaluation of demographic and other baseline data and all safety parameters including adverse events, physical examination, evaluation of vital signs, previous and current therapy, ECG and all the rest instrumental examination methods, all laboratory investigations. • Population for single dosing pharmacokinetics evaluation consists of all participants who administered the test drug and have at least 1 measure of the test drug concentration. Calculation of PK parameters and their statistical processing will be performed on this population. • Population for multiple dosing pharmacokinetics evaluation consists of all participants who administered the test drug at least 7 times and have measure of the test drug concentration after the first and seventh administration of the test drug. For multiple dosing cohorts, calculation of PK parameters and their statistical

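### In cohorts C6 and C7, the seven-dose rule for the PK population leaves early stoppers' complete dose-1 profiles out of the dose-1 summaries

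*Combined protocol and SAP*

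**What the plan says.** All references are to section 1, Study summary, of the combined protocol and SAP.

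- **PK population for multiple dosing (Statistical methods).** The definition reads: "all participants who administered the test drug at least 7 times and have measure of the test drug concentration after the first and seventh administration". The next sentence, which begins "For multiple dosing cohorts, calculation of PK parameters and their statistical" and runs over a page break, assigns both the calculation and the statistical processing for these cohorts to that population. It makes no exception for dose 1.
- **PK population for single dosing (same row).** Volunteers must have been dosed and "have at least 1 measure of the test drug concentration".
- **Sampling in Stage 2 (Design and methodology).** "Before and after the administration of the first, 7th and last (14th) dose of the test drug, venous blood will be taken from the volunteers", with time points out to 24 h after each of these three doses. After premature withdrawal, "attempts to sample their blood according to schedule for the last (14) dose will be taken".
- **Parameters (Primary and secondary variables, multiple dosing).** Cmax, Tmax and AUC0-t are listed separately from their steady-state counterparts.
- **Withdrawn volunteers (Withdrawal criteria).** "If patient is withdrawn from the study due to any reason, all biosamples collected will be analyzed". On replacement: "In each of cohorts C6-C7, a volunteer can be substituted only if two or more volunteers are withdrawn". The Stage 2 design text also excepts dropouts for AE/SAE from additional enrolment.
- **Cohort size (Planned number of study subjects).** Six main-group volunteers in each of C6 and C7.

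**The concern.** A dose-1 profile is complete 24 h after the first dose. Nothing that happens at doses 2 to 7 changes its Cmax, Tmax or AUC. The population rule nevertheless makes its use depend on the volunteer still taking part at dose 7. The plan therefore collects and assays a valid profile and then leaves it out of the summary it was collected for.

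Two things are at stake. The first is precision, because each cohort has only six volunteers and a single loss is not made good. The second is selection. If volunteers with unusually high (or low) exposure are more likely to stop early, the dose-1 summary describes only those who stayed, and its mean is shifted. The Design and methodology row says the study results will be used to plan later studies, so the dose-1 summaries should rest on all the valid data.

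**Working it through.** **Step 1: does the text exclude the early stopper?** Take a C6 volunteer who completes the dose-1 profile and stops after dose 3.

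| Provision | Result for him |
|---|---|
| Stage 2 sampling | 24 h profile after dose 1 taken |
| Samples of withdrawn volunteers | Assayed |
| Multiple-dose PK population | Not met: 3 doses, and no concentration after dose 7 |
| PK calculation and statistics for C6-C7 | Run on that population only, so he is in no dose-1 summary |
| Substitution | None if he is the only withdrawal |
| Safety population | Included (at least one dose) |

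The single-dose population, read alone, would admit him, because its wording is not limited to C1-C5. The sentence specific to the multiple-dose cohorts overrides that reading. If the sponsor meant otherwise, the two definitions conflict and the wording still needs correcting.

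**Step 2: precision.** The plan gives no precision or power figure to reproduce. With one of 6 left out and exposure unrelated to stopping, the standard error changes by sqrt(6/5) - 1 = 1.095 - 1 = +9.5%, or about 10%. At an assumed between-subject CV of 40% (log-normal), the 90% confidence limits of the geometric mean lie a factor of 1.37 either side at n = 6 and 1.44 at n = 5.

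**Step 3: bias if stopping is related to exposure.** Set the five who stay at exposure 1 and the stopper at r. The reported mean is 1 and the six-person mean is (5 + r)/6, so the relative error is 6/(5 + r) - 1.

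| r (assumed) | Calculation | Error in dose-1 mean |
|---|---|---|
| 0.5 | 6/5.5 - 1 | +9.1% |
| 1 | 6/6 - 1 | 0 |
| 2 | 6/7 - 1 | -14.3% |

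As a cross-check on the geometric mean, I simulated cohorts of six in which the stopper is always the volunteer with the highest exposure. The expected ratio of the reported to the full-cohort geometric mean is 0.95, 0.91 and 0.87 at CVs of 20%, 40% and 60%.

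**Step 4: scale.** At an assumed CV of 30% to 50%, the standard error of a six-person mean is 0.30/sqrt(6) = 12.2% to 0.50/sqrt(6) = 20.4%. The shifts in step 3 are within or near one standard error.

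**Step 5: how often.** The documents give no early-stopping rate. At assumed rates of 5%, 10% and 20% before dose 7, the chance that exactly one of six stops (the case with no substitution) is 6p(1 - p)^5 = 23%, 35% and 39%.

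**The case against.** The strongest defence is that a multiple-dose PK population exists to compare first-dose with repeated-dose exposure in the same volunteers, and requiring profiles after doses 1 and 7 keeps that comparison clean. This is a fair aim, but it does not require dropping valid dose-1 profiles from the dose-1 summary. The comparison can be restricted to volunteers with both profiles. The present rule does not give equal numbers throughout either: it does not ask for a dose-14 profile, so a volunteer who stops between doses 7 and 13 is in the population without one.

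A second defence is that Stage 1 already supplies single-dose fasting PK. If Stage 2 uses the two highest single doses, as the dose justification presumes, those doses were each given to six volunteers and sampled to 48 h or 72 h, against 24 h after dose 1 in C6-C7. This lowers the weight of the point. It is not a reason to omit valid profiles, and the Stage 2 doses are not fixed in the text.

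Third, large shifts need unlikely volunteers. At r = 3 the formula gives 6/8 - 1 = -25%, but under a log-normal distribution with CV 30% to 50% such a volunteer lies about 3.7 to 2.3 standard deviations above the median. That figure is an extreme and should not be quoted as typical. Even r = 2 lies about 2.4 standard deviations out at CV 30%.

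A reader might also infer more than the documents support:

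- **That the data are lost, or safety is affected.** The samples are assayed, the restriction is on PK calculation and statistics, and anyone dosed once is in the safety population.
- **That early trough summaries are affected.** The parameter list names only trough concentration after multiple administration. No summary for days 3 to 6 is specified.
- **That Stage 2 doses could be chosen wrongly.** They are set before C6-C7 data exist, with tolerance and DLT as the defining criteria.
- **That vomited-dose profiles are mishandled.** "Vomiting during the first 4 hours after the drug administration" is a withdrawal criterion, and the PK population definitions do not mention it. This is a silence in a study summary. Keeping such a profile is not always worse than excluding it, and disposition listings, adverse events and individual curves would let a reader identify it. At most it is a query to the sponsor.

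**Conclusion.** The point holds as a minor weakness in the analysis plan. By its wording, section 1 leaves a C6-C7 volunteer who stops after one to six doses out of the dose-1 Cmax, Tmax and AUC summaries, even with a complete, assayed dose-1 profile.

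The textual conclusion needs no assumption, but it rests on section 1 only, which is the text available here. The size does rest on assumptions. One early stopper in six raises the standard error by about 10% if exposure and stopping are unrelated. If they are related, the dose-1 mean is off by about +9% (stopper at half typical exposure) to -14% (at twice). If nobody stops before dose 7, the effect is zero. PK is reported descriptively and individual curves are plotted, so no test or decision rule in the plan depends on it.

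**What to change.** Change the analysis wording only:

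1. For C6 and C7, define PK evaluability by profile. Dose-1, dose-7 and dose-14 parameters are each calculated and summarised in every volunteer with an evaluable profile for that dose. State in advance what makes a profile evaluable.
2. Report changes from dose 1 to dose 7 or dose 14 only within volunteers who have both profiles, and show n in each table.
3. List profiles taken at early withdrawal under the actual number of the last dose, and do not pool them with dose 14, although they follow the dose-14 sampling schedule.

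Separately, ask the sponsor how profiles with vomiting inside the protocol's own 4 h window will be flagged in the PK summaries.

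The cost is a few sentences in the SAP, with no added samples or assays and no change to the conduct of the trial. The downside is that n may differ between the dose-1, dose-7 and dose-14 tables; item 2 keeps comparisons between doses valid.
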